14.3 Quality Assurance Audits and Regulatory Agency Inspections

The study site also may be subject to quality assurance audits by the sponsor or designees. In this circumstance, the sponsor-designated auditor will contact the site in advance to arrange an auditing visit. The auditor may ask to visit the facilities where laboratory samples are collected, where the medication is stored and prepared, and any other facility used during the study. In addition, there is the possibility that this study may be inspected by regulatory agencies, including those of foreign governments (eg, the Food and Drug Administration [FDA], the United Kingdom Medicines and Healthcare products Regulatory Agency [MHRA], the Pharmaceuticals and Medical Devices Agency of Japan [PMDA]). If the study site is contacted for an inspection by a regulatory body, the sponsor should be notified immediately. The investigator and institution guarantee access for quality assurance auditors to all study documents as described in Section 14.1.

15.0 ETHICAL ASPECTS OF THE STUDY

This study will be conducted with the highest respect for the individual participants (ie, subjects) according to the protocol, the ethical principles that have their origin in the Declaration of Helsinki, and the ICH Harmonised Tripartite Guideline for GCP. Each investigator will conduct the study according to applicable local or regional regulatory requirements and align his or her conduct in accordance with the “[Responsibilities of the Investigator](#)” that are listed in [Appendix E](#). The principles of Helsinki are addressed through the protocol and through appendices containing requirements for informed consent and investigator responsibilities.

15.1 IRB Approval

IRBs must be constituted according to the applicable local requirements. The sponsor or designee will require documentation noting all names and titles of members who make up the respective IRB. If any member of the IRB has direct participation in this study, written notification regarding his or her abstinence from voting must also be obtained.

The sponsor or designee will supply relevant documents for submission to the respective IRB for the protocol’s review and approval. This protocol, the Investigator’s Brochure, a copy of the informed consent form, and, if applicable, subject recruitment materials and/or advertisements and other documents required by all applicable laws and regulations, must be submitted to a central or local IRB for approval. The IRB’s written approval of the protocol and subject informed consent must be obtained and submitted to the sponsor or designee before commencement of the study (ie, before shipment of the sponsor-supplied drug or study specific screening activity). The IRB approval must refer to the study by exact protocol title, number, and version date; identify versions of other documents (eg, informed consent form) reviewed; and state the approval date. The sponsor will notify site once the sponsor has confirmed the adequacy of site regulatory documentation. Until the site receives notification no protocol activities, including screening may occur.

Sites must adhere to all requirements stipulated by their respective IRB. This may include notification to the IRB regarding protocol amendments, updates to the informed consent form, recruitment materials intended for viewing by subjects, local safety reporting requirements, reports and updates regarding the ongoing review of the study at intervals specified by the respective IRB, and submission of the investigator’s final status report to IRB. All IRB approvals and relevant documentation for these items must be provided to the sponsor or its designee.

Subject incentives should not exert undue influence for participation. Payments to subjects must be approved by the IRB and sponsor.

Regarding PGx investigation using collected and stored specimens, analysis will be carried out at the time when detail is determined. The sponsor will create a research protocol for PGx investigations and a research protocol will require prior approval of the company IRB in Japan.

15.2 Subject Information, Informed Consent, and Subject Authorization

Written consent documents will embody the elements of informed consent as described in the Declaration of Helsinki and the ICH Guidelines for GCP and will be in accordance with all

applicable laws and regulations. The informed consent form describes the planned and permitted uses, transfers, and disclosures of the subject's personal and personal health information for purposes of conducting the study. The informed consent form further explains the nature of the study, its objectives, and potential risks and benefits, as well as the date informed consent is given. The informed consent form will detail the requirements of the participant and the fact that she is free to withdraw at any time without giving a reason and without prejudice to her further medical care.

The investigator is responsible for the preparation, content, and IRB approval of the informed consent form. The informed consent form must be approved by the IRB prior to use.

The informed consent form must be written in a language fully comprehensible to the prospective subject. It is the responsibility of the investigator or subinvestigator to explain the detailed elements of the informed consent form to the subject. Information should be given in both oral and written form whenever possible and in the manner deemed appropriate by the IRB.

The subject must be given ample opportunity to: (1) inquire about details of the study and (2) decide whether or not to participate in the study. If the subject determines she will participate in the study, then the informed consent form must be signed and dated by the subject at the time of consent and prior to the subject entering into the study. The subject should be instructed to sign using their legal names, not nicknames, using blue or black ballpoint ink. The investigator or subinvestigator must also sign and date the informed consent form at the time of consent and prior to subject entering into the study.

Once signed, the original informed consent form will be stored in the investigator's site file. The investigator or subinvestigator must document the date the subject signs the informed consent in the subject's medical record. Copies of the signed informed consent form shall be given to the subject.

All revised informed consent forms must be reviewed and signed by relevant subjects in the same manner as the original informed consent. The date the revised consent was obtained should be recorded in the subject's medical record, and the subject should receive a copy of the revised informed consent form.

PGx research should be explained to the subject using "Informed Consent Form for PGx Research of TAK-385" after explanation about the study using the informed consent form has been given. Specimens for PGx research should be collected from subjects who consented to participate in the study and PGx research.

The procedure specified in Section 9.4 should be followed when a subject requests disposal of her PGx samples.

15.3 Subject Confidentiality

The sponsor and designees affirm and uphold the principle of the subject's right to protection against invasion of privacy. Throughout this study, a subject's source data will only be linked to the sponsor's clinical study database or documentation via a unique identification number. As permitted by all applicable laws and regulations, limited subject attributes, such as sex, age or

date of birth may be used to verify the subject and accuracy of the subject's unique identification number.

To comply with ICH Guidelines for GCP and to verify compliance with this protocol, the sponsor requires the investigator to permit its monitor or designee's monitor, representatives from any regulatory authority (eg, FDA, MHRA, PMDA), the sponsor's designated auditors, and the appropriate IRBs to review the subject's original medical records (source data or documents), including, but not limited to, laboratory test result reports, ECG reports, admission and discharge summaries for hospital admissions occurring during a subject's study participation, and autopsy reports. Access to a subject's original medical records requires the specific authorization of the subject as part of the informed consent process (see Section 15.2).

Copies of any subject source documents that are provided to the sponsor must have certain personally identifiable information removed (ie, subject name, address, and other identifier fields not collected on the subject's eCRF).

15.4 Publication, Disclosure, and Clinical Trial Registration Policy

15.4.1 Publication and Disclosure

The investigator is obliged to provide the sponsor with complete test results and all data derived by the investigator from the study. During and after the study, only the sponsor may make study information available to other study investigators or to regulatory agencies, except as required by law or regulation. Except as otherwise allowable in the clinical study site agreement, the protocol or study results are the sole responsibility of the sponsor.

The sponsor may publish any data and information from the study (including data and information generated by the investigator) without the consent of the investigator.

The investigator and subinvestigator need to obtain a prior written approval from the sponsor to publish any information from the study externally such as to a professional association.

15.4.2 Clinical Trial Registration

In order to ensure that information on clinical trials reaches the public in a timely manner and to comply with applicable laws, regulations and guidance, Takeda will, at a minimum register interventional clinical trials it sponsors anywhere in the world on ClinicalTrials.gov or other publicly accessible websites before start of study, as defined in Takeda Policy/Standard. Takeda contact information, along with investigator's city, country, and recruiting status will be registered and available for public viewing.

15.4.3 Clinical Trial Results Disclosure

Takeda will post the results of clinical trials on ClinicalTrials.gov or other publicly accessible websites, as required by Takeda Policy/Standard, applicable laws and/or regulations.

15.5 Insurance and Compensation for Injury

Each subject in the study must be insured in accordance with the regulations applicable to the site where the subject is participating. If a local underwriter is required, then the sponsor or sponsor's designee will obtain clinical study insurance against the risk of injury to clinical study subjects. Refer to the Clinical Study Site Agreement regarding the sponsor's policy on subject compensation and treatment for injury. If the investigator and subinvestigator have questions regarding this policy, he or she should contact the sponsor or sponsor's designee.

3.0 LIST OF ABBREVIATIONS

AE	adverse event
AESI	adverse event of special interest
ALP	alkaline phosphatase
ALT	alanine aminotransferase
AST	aspartate aminotransferase
AUC	area under the blood concentration-time curve
BAP	bone specific alkaline phosphatase
BMD	bone mineral density
BMI	body mass index
BUN	blood urea nitrogen
C _{max}	maximum observed plasma concentration
CRF	case report form
CRO	contract research organization
CT	computed tomography
DXA	dual-energy x-ray absorptiometry
E ₂	estradiol
ECG	electrocardiogram
eCRF	electronic case report form
FAS	full analysis set
FDA	Food and Drug Administration
Fe	iron
FSH	follicle-stimulating hormone
GCP	Good Clinical Practice
GGT	gamma glutamyl transferase
GLDH	glutamate dehydrogenase
GnRH	gonadotropin-releasing hormone
hCG	human chorionic gonadotropin
HCT	hematocrit
HDL	high density lipoprotein
HGB	hemoglobin
ICH	International Conference on Harmonisation
INN	international non-proprietary name
INR	international normalized ratio
IRB	institutional review board
IUD	intrauterine device
LDH	lactate dehydrogenase
LDL	low density lipoprotein
LFT	liver function test
LH	luteinizing hormone
MedDRA	Medical Dictionary for Regulatory Activities

MHRA	Medicines and Healthcare products Regulatory Agency
MRI	magnetic resonance imaging
NILM	negative for intraepithelial lesion or malignancy
NRS	numerical rating scale
NSAIDs	non-steroidal anti-inflammatory drugs
NTELOP	N-telopeptide
P	progesterone
PBAC	pictorial blood loss assessment chart
P-gp	P-glycoprotein
PGx	pharmacogenomics
PMDA	Pharmaceuticals and Medical Devices Agency
PPS	per protocol set
PT	preferred term
PTE	Pretreatment event
QOL	quality of life
Run-in AE	run-in adverse event
RBC	red blood cell
SAE	serious adverse event
SAP	statistical analysis plan
SC	subcutaneous(ly)
SERM	selective estrogen receptor modulator
SOC	system organ class
SUSARs	suspected unexpected serious adverse reactions
TBA	total bile acid
TEAE	treatment-emergent adverse event
TPC	Takeda Pharmaceutical Company Limited
UFS-QOL	uterine fibroid symptom and quality of life
ULN	upper limit of normal
WBC	white blood cell
WHO	World Health Organization
WPAI:GH	Work Productivity and Activity Impairment Questionnaire:General Health

4.0 OBJECTIVES

4.1 Primary Objectives

The primary objective of this study is to evaluate the efficacy of TAK-385 40 mg administered orally once daily for 12 weeks, compared with leuprorelin injection (once/4 weeks, 1.88 mg or 3.75 mg subcutaneously [SC]/time) in subjects with uterine fibroids.

4.2 Secondary Objectives

The secondary objective of this study is to evaluate the efficacy and safety of TAK-385 40 mg administered orally once daily for 24 weeks, compared with leuprorelin injection (once/4 weeks, 1.88 mg or 3.75 mg SC/time) in subjects with uterine fibroids.

4.3 Additional Objectives

An additional objective of this study is to evaluate the pharmacodynamic effect, which is blood concentrations of luteinizing hormone (LH), follicle-stimulating hormone (FSH), estradiol (E₂), and progesterone (P).

4.4 Study Design

An overview of the study design is shown in Figure 4

4.4.1 Study Population and Design

This is a phase 3, multicenter, randomized, double-blind, parallel-group, non-inferiority study to evaluate the efficacy and safety of TAK-385 compared with leuprorelin injection (once/4 weeks, 1.88 mg or 3.75 mg SC/time) in premenopausal subjects \geq 20 years of age with symptomatic uterine fibroids. The primary objective is to evaluate the efficacy of TAK-385 40 mg administered orally once daily for 12 weeks. The secondary objective is to evaluate the efficacy and safety of TAK-385 40 mg administered orally once daily for 24 weeks. In addition, the pharmacodynamics of continuous oral administration of TAK-385 40 mg for 24 weeks is to be assessed.

Subjects must be diagnosed to have uterine fibroids as confirmed by transvaginal ultrasound or other methods, and have symptoms of menorrhagia (the total pictorial blood loss assessment chart [PBAC] score of \geq 120 for the entire menstrual cycle immediately before VISIT 3). The total number of subjects to be randomized under double-blind conditions is 288 (144 subjects each for the TAK-385 40 mg group or leuprorelin group).

After signing the informed consent form, subjects will start recording in the patient diary from the day of VISIT 1. During the period between VISIT 2 and VISIT 3, in which subjects must experience 1 menstrual cycle, the baseline values for the efficacy evaluation, including PBAC scores and pain symptoms (baseline PBAC score: the total PBAC score for the entire menstrual cycle immediately before VISIT 3) will be collected. Subjects should record in the patient diary every day until the end of study drug administration. VISIT 2 should be between the first and

fifth day of the first menstruation after VISIT 1. The study drug (TAK-385 placebo and leuprorelin placebo) will be administered under single-blind conditions from the day of VISIT 2 to the day before VISIT 3. VISIT 3 should be between the first and fifth day of the second menstruation after VISIT 1. From VISIT 3 to 10, subjects will receive study drug (TAK-385 and leuprorelin placebo, or TAK-385 placebo and leuprorelin) in a double blind manner. Subjects should try to visit the study site during the morning in a fasted state and before taking the TAK-385 tablet.

The study consists of Screening of approximately 1 to 6 weeks, a Run-in period of 3 to 6 weeks, a Treatment period of 24 weeks, and a Follow-up period of 4 weeks. The total period of study participation is approximately 32 to 40 weeks. If the recovery of the first post-treatment menstruation is not observed by the visit at the end of the Follow-up (VISIT 11), the subject will undergo further follow-up using possible means such as by telephone interview, until the recovery of the first post-treatment menstruation is observed. During the course of this study, subjects will visit the study site to undergo the designated examinations and evaluations at each visit, every 2 weeks for a month after the initiation of study drug administration (VISIT 3) under double-blind conditions, and monthly thereafter.

[figure not shown]
4.4.2 Dose Level and Regimen

At VISIT 3, subjects will be randomized in a 1:1 ratio to either the TAK-385 40 mg group or leuprorelin group. Study drug (TAK-385 40 mg + leuprorelin placebo or TAK-385 placebo + leuprorelin) will be administered in a double-dummy method from the day of VISIT 3 to the day before VISIT 10 (or until early termination) under double-blind conditions.

The investigator or subinvestigator will decide the dosage of leuprorelin at VISIT 2 in accordance with the approved dosage and administration, considering the body weight and symptoms of the individual subject. Leuprorelin (or leuprorelin placebo) should be administered SC (injection) once every 4 weeks using the same dose throughout the Run-in and Treatment.

TAK-385 (or TAK-385 placebo) will be administered daily as a single oral dose before breakfast.

Figure 4 Schematic of Study Design

5.0 ANALYSIS ENDPOINTS

5.1 Primary Endpoint

1) Efficacy:

Proportion of subjects with a total PBAC score of < 10 from Week 6 to 12

5.2 Secondary Endpoints

1) Efficacy:

- Proportion of subjects with a total PBAC score of < 10 (from Week 2 to 6, from Week 18 to 24, and for 6 weeks before the final dose of study drug)
- Myoma volumes (Week 2, 4, 8, 12 and 24)

Note: Only the largest myoma among those measurable at VISIT 1 will be measured throughout the study.

- Uterine volumes (Week 2, 4, 8, 12 and 24)
- Hemoglobin (HGB) (Week 4, 8, 12, 16, 20, 24 and Follow-up)
- Numerical Rating Scale (NRS) score (from Week 6 to 12, from Week 2 to 6, from Week 18 to 24, and for 6 weeks before the final dose)
- Uterine fibroid symptom and QOL (UFS-QOL) score (Week 4, 8, 12, 16, 20, 24 and Follow-up)

2) Safety:

- Adverse events (AEs), vital signs, weight, standard 12-lead electrocardiogram (ECG), clinical laboratory tests, bone mineral density (BMD), biochemical bone metabolism markers (serum N-telopeptide [NTELOP] and bone specific alkaline phosphatase [BAP])

5.3 Additional Endpoints

1) Efficacy:

- Hematocrit (HCT), serum iron (Fe), and serum ferritin (Week 4, 8, 12, 16, 20, 24 and Follow-up)
- Use of analgesic medications during the Treatment (from Week 6 to 12, from Week 2 to 6, from Week 18 to 24, and for 6 weeks before the final dose)
- Work Productivity and Activity Impairment Questionnaire:General Health (WPAI:GH) (Week 2, 4, 8, 12 and 24)

2) Safety:

- Period from the last dose of study drug to return of menstrual cycles

3) Pharmacodynamic effects:
LH, FSH, E₂ and P (Week 2, 4, 8, 12, 16, 20, 24 and Follow-up)

6.0 DETERMINATION OF SAMPLE SIZE

Justification of Sample size

In a clinical study of ulipristal acetate (already approved in Europe) compared with leuprorelin conducted overseas, the proportion of subjects with a total PBAC score of < 75 for 28 days before Week 13 was 89.1% in the TAP-144-SR (1M) 3.75 mg group, and the proportion of subjects with a total PBAC score of ≤ 2 for 28 days before Week 13 was 80.4%.

In TAK-385 phase 2 study in the treatment of uterine fibroids, the point estimate (and corresponding 2-sided 95% confidence interval) of the proportion of subjects with a total PBAC score of < 10 from Week 6 to 12 was 83.6% (71.2%, 92.2%) in the TAK-385 40 mg group.

Based on the results of the above 2 studies, the proportions of subjects with a total PBAC score of < 10 from Week 6 to 12 in both TAK-385 40 mg group and leuprorelin group are estimated to be 83.6%.

Under this assumption, a sample size of at least 129 subjects per group will provide $\geq 90\%$ power to demonstrate non-inferiority at 1-sided 0.025 level of significance, using a non-inferiority margin of 15% (nQuery Advisor 6.01).

Based on the above, a sample size of 129 subjects per group (258 subjects in total) is planned as the number of evaluable subjects. Assuming that approximately 10% of subjects will not be evaluable for the primary endpoint, 144 subjects are to be randomized to each group, for a total of 288 subjects.

Justification of non-inferiority margin

As the result of the TAK-385 phase 2 study in the treatment of uterine fibroids, the point estimate (and corresponding 2-sided 95% confidence interval) of the difference in the proportion of subjects with a total PBAC score of < 10 from Week 6 to 12 was 83.6% (73.9%, 93.4%) between the TAK-385 40 mg group and Placebo group. Assuming that leuprorelin has comparable effect to TAK-385 40 mg, the non-inferiority margin of 15% is considered smaller than the smallest effect size that leuprorelin would be reliably expected to have.

7.0 METHODS OF ANALYSIS AND PRESENTATION

7.1 General Principles

All statistical analyses will be conducted using SAS® Version 9.2, or higher.

A statistical test for the primary endpoint will be reported as 1-sided and will be assessed at $\alpha=0.025$ significance level and all confidence intervals will be reported as 2-sided unless otherwise stated. P-values will be rounded to 4 decimal places prior to assessment of statistical significance.

Means and medians will be presented to 1 more decimal place than the recorded data. The standard deviations (SDs) will be presented to 2 more decimal places than the recorded data. Confidence intervals about a parameter estimate will be presented using the same number of decimal places as the parameter estimate.

Where appropriate, variables will be summarized descriptively by study visit. For the categorical variables, the count and proportions of each possible value will be tabulated by treatment group. The denominator for the proportion will be based on the number of subjects who provided non-missing responses to the categorical variable. For continuous variables, the number of subjects with non-missing values, mean, median, SD, minimum, and maximum values will be tabulated. Confidence intervals for continuous variables will be calculated based on t-statistics and ones for categorical variables will be based on Wald confidence intervals without using any model, unless otherwise stated.

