13.3 Determination of Sample Size

Justification of Sample size

In a clinical study of ulipristal acetate (already approved in Europe) compared with leuprorelin conducted overseas, the proportion of subjects with a total PBAC score of < 75 for 28 days before Week 13 was 89.1% in the TAP-144-SR (1M) 3.75 mg group, and the proportion of subjects with a total PBAC score of ≤ 2 for 28 days before Week 13 was 80.4%.

In TAK-385 phase 2 study in the treatment of uterine fibroids, the point estimate (and corresponding 2-sided 95% confidence interval) of the proportion of subjects with a total PBAC score of < 10 from Week 6 to 12 was 83.6% (71.2%, 92.2%) in the TAK-385 40 mg group.

Based on the results of the above 2 studies, the proportions of subjects with a total PBAC score of < 10 from Week 6 to 12 in both TAK-385 40 mg group and leuprorelin group are estimated to be 83.6%.

Under this assumption, a sample size of at least 129 subjects per group will provide $\geq 90\%$ power to demonstrate non-inferiority at 1-sided 0.025 level of significance, using a non-inferiority margin of 15% (nQuery Advisor 6.01).

Based on the above, a sample size of 129 subjects per group (258 subjects in total) is planned as the number of evaluable subjects. Assuming that approximately 10% of subjects will not be evaluable for the primary endpoint, 144 subjects are to be randomized to each group, for a total of 288 subjects.

Justification of non-inferiority margin

As the result of the TAK-385 phase 2 study in the treatment of uterine fibroids, the point estimate (and corresponding 2-sided 95% confidence interval) of the difference in the proportion of subjects with a total PBAC score of < 10 from Week 6 to 12 was 83.6% (73.9%, 93.4%) between the TAK-385 40 mg group and Placebo group. Assuming that leuprorelin has comparable effect to TAK-385 40 mg, the non-inferiority margin of 15% is considered smaller than the smallest effect size that leuprorelin would be reliably expected to have.

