7.8 Efficacy Analysis

7.8.1 Primary Efficacy Endpoint(s)

7.8.1.1 Primary Analysis

Analysis Set: Full Analysis Set

Analysis

Variable(s): Proportion of subjects with a total PBAC score of < 10 from Week 6 to 12

Analytical Method(s): The point estimate and 2-sided 95% confidence interval of the proportion of subjects with a total PBAC score of < 10 from Week 6 to 12 will be summarized by treatment group. The point estimate and 2-sided 95% confidence interval of the difference in the percentage will be calculated between TAK-385 40 mg group and leuprorelin group (TAK-385 40 mg group – leuprorelin group), using Farrington and Manning (FM) method. In addition, non-inferiority test using FM method with a non-inferiority margin of 15% will be conducted for the comparison between TAK-385 40 mg group and leuprorelin group. If the lower bound of the 95%CI is greater or equal to the non-inferiority margin of -15%, then non-inferiority of TAK-385 40mg to leuprorelin will be concluded.

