7.8.1.4 Examination of Subgroups

Analysis Set: Full Analysis Set

Analysis

Variable(s): Proportion of subjects with a total PBAC score of < 10 from Week 6 to 12

Subgroup(s): Age (years) [20<= - <30, 30<= - <40, 40<= - <50, 50<= - <=Max]

BMI (kg/m^2) at Baseline [Min<= - <18.5, 18.5<= - <25.0, 25.0<= - <=Max]

PBAC Score at Baseline [120<= - <200, 200<= - <500, 500<= - <=Max]

Birth Experience [Yes, No]

Volume of Uterus at Baseline (cm^3) [Min<= - <=28, 28< - <=170, 170< - <=700, 700< - <=Max]

Type of Uterine Fibroid Subserosal Fibroid [Yes, No]

Intramural Fibroid [Yes, No]

Submucosal Fibroid [Yes, No]

Analytical

Method(s): (1) Descriptive Statistics

The point estimate and 2-sided 95% confidence interval of the proportion of subjects with a total PBAC score of < 10 from Week 6 to 12 will be summarized for above each subgroup by treatment group.

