7.8.2.3 Hemoglobin

Analysis Set: Full Analysis Set

Analysis

Variable(s): HGB (g/dL) [Min<= - <12, 12<= - <=Max]

Change from baseline on HGB [Min<= - <1, 1<= - <=Max]
(g/dL)

Subgroup(s): Oral iron preparation use at [Yes, No]
baseline

HGB at Baseline (g/dL) [Min<= - <12, 12<= - <=Max]

Visit: Baseline, Week 4, 8, 12, 16, 20, 24 and Follow-up

Analytical

Method(s): Summary statistics will be provided for the observed values and the changes from baseline by treatment group for each visit.

The mean differences in the change from baseline between TAK-385 40 mg and leuprorelin groups and the two-sided 95% confidence intervals will be provided for each visit.

For categorical variables, frequency will be summarized by treatment group for each visit. The differences in the percentage between TAK-385 40 mg and leuprorelin groups and the two-sided 95% confidence intervals will be provided for each visit.

Additionally, the above mentioned analysis will also be conducted for each subgroup.

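### The SAP's default Wald interval applies to the per-arm and subgroup confidence intervals of the primary response rate; the effect is small in the full arms but serious in any sparse subgroup cell

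*SAP*

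**What the plan says.** SAP 7.1 (General Principles) fixes the interval method wherever a later section is silent. For categorical variables, "ones for categorical variables will be based on Wald confidence intervals without using any model, unless otherwise stated".

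SAP 7.8.1.1 (Primary Analysis) then asks for two kinds of interval. The first is per arm: "The point estimate and 2-sided 95% confidence interval of the proportion of subjects with a total PBAC score of < 10" over Weeks 6 to 12, with no method named. The second is for the difference between arms, and only there does the text add "using Farrington and Manning (FM) method". The non-inferiority rule and test use that second interval and the same method. SAP 7.8.1.2 repeats the analysis in the per protocol set.

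SAP 7.8.1.4 (Examination of Subgroups) asks for the same single-proportion interval, which "will be summarized for above each subgroup by treatment group". It lists four age bands, three BMI bands, three baseline PBAC bands, birth experience (yes/no), four uterine-volume bands and three fibroid types (each yes/no). It names no interval method.

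For the same endpoint in phase 2, Protocol 13.3 and SAP 6.0 report "83.6% (71.2%, 92.2%) in the TAK-385 40 mg group".

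**The concern.** FM is a two-sample method and cannot supply a single-arm interval, and nothing else in the SAP overrides the default. The per-arm and subgroup intervals are therefore Wald.

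The Wald interval is known to behave badly when a proportion is near 0 or 1 and the sample is small. Here the planned rate is 83.6%, and 7.8.1.4 divides each arm into up to four bands per factor. Three faults could follow: coverage below the stated 95%, upper limits above 100%, and a zero-width interval when every woman in a cell responds. Readers use these intervals to judge how far to trust a subgroup estimate, and a zero-width interval presents a rate from a handful of women as known without error.

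**Working it through.** **Inputs.** Planned rate of 83.6% in both arms, 129 evaluable and 144 randomized per arm, and the phase 2 interval (Protocol 13.3, SAP 6.0). Interval default from SAP 7.1. Subgroup sizes are in neither document; 5 to 60 women per arm and cell are assumed.

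**The plan's own figures.** For x responders among n women, p = x/n and the Wald interval is p ± 1.96·√[p(1−p)/n]. The only count from n = 20 to 199 that gives 83.6% with Clopper-Pearson limits of 71.2% and 92.2% is 46/55. The count and the method are inferred; neither is stated. On 46/55:
- Clopper-Pearson: 71.2% to 92.2% (the stated phase 2 interval for the arm)
- Wilson: 71.7% to 91.1%
- Wald: 0.8364 ± 1.96·√(0.8364·0.1636/55) = 0.8364 ± 0.0978, or 73.9% to 93.4%

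The Wald result equals the interval that the documents give for the phase 2 difference from placebo, as expected if no placebo subject responded. Its lower limit is 2.7 points above the exact one.

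**Coverage.** Exact coverage at a true rate π is the sum of Binomial(x; n, π) over all x whose interval contains π. At π = 83.6%:

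| n per arm | Wald | Wilson | Clopper-Pearson | Chance that all respond (π^n) |
|---|---|---|---|---|
| 144 | 93.4% | 95.8% | 96.8% | about 0 |
| 129 | 93.2% | 95.7% | 96.9% | about 0 |
| 60 | 92.9% | 94.8% | 96.3% | about 0 |
| 40 | 90.3% | 97.0% | 97.0% | 0.1% |
| 30 | 87.3% | 94.9% | 97.8% | 0.5% |
| 20 | 85.3% | 93.8% | 99.0% | 2.8% |
| 15 | 92.6% | 97.5% | 99.4% | 6.8% |
| 10 | 81.9% | 93.4% | 98.6% | 16.7% |
| 5 | 55.8% | 96.6% | 99.7% | 40.8% |

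Coverage oscillates with n and π, so the 92.6% at n = 15 should not be read as safe. Averaged over true rates of 75% to 95%, Wald covers 75.1% (n = 10), 82.7% (n = 15), 86.7% (n = 20), 90.1% (n = 30), 92.1% (n = 60), 93.7% (n = 129) and 93.9% (n = 144).

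**Full-arm limits.** For 108/129 (83.7%), Wald gives 77.4% to 90.1%, Wilson 76.4% to 89.1% and Clopper-Pearson 76.2% to 89.6%. The limits move by between 0.5 and 1.2 points.

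**Small-cell limits.** Wald gives 71.4% to 108.6% for 9/10 and 85.4% to 104.6% for 19/20. At n = 20 and 83.6%, the upper limit exceeds 100% in 55% of samples. For 10/10 Wald gives 100% to 100%, while the lower limit is 72.2% by Wilson and 69.2% by Clopper-Pearson.

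**The case against.** The strongest reply is that nothing is decided on these intervals. Non-inferiority rests on the FM interval and FM test, and 7.8.1.4 is labelled descriptive and asks for no between-arm comparison. That stands. A reader might infer that the primary conclusion, the type I error or the sample size is compromised; the documents do not support this.

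A reader might also infer that the overall response rates carry seriously wrong error bars. They do not. The full-arm shortfall averages about 1 point over true rates of 75% to 95%. A lower figure can be found, 88.5% at n = 129 with a true rate of 95%, but it is an unfavourable point on an oscillating curve: it becomes 94.2% at n = 125 and 92.7% at n = 144. The plan assumes 83.6%, not 95%.

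The severe figures do depend on assumed cell sizes, and counting categories does not show that many cells are small. A few sparse cells are plausible. Women of 50 or over must still be premenopausal with regular cycles, and the lowest uterine-volume band stops at 28 cm³ although every woman must have a myoma of at least 3 cm (as a sphere, π/6 · 3³ = 14.1 cm³). That is an expectation, not a documented fact.

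It is tempting to extend the point to SAP 7.8.2.3, where for hemoglobin "The differences in the percentage between TAK-385 40 mg and leuprorelin groups and the two-sided 95% confidence intervals will be provided for each visit". The case is not made. Wald intervals for that difference were near nominal in most cases run. The poor figure, 79.6%, needs about 10 women per arm with rates of 95% and 85%; the same rates give 94.0% at 20 per arm and 94.5% at 60. Failure also occurs if both arms are at 100%.

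Finally, the method apparently used in phase 2 does not bind this SAP. The mismatch hinders comparison with the earlier result but is not an error in itself.

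**Conclusion.** The point holds as a limited one about descriptive intervals. That Wald governs them follows directly from the SAP text. In the full arms the cost is about 1 to 2 points of coverage at the planned rate and about 1 point in the limits, and an observed 100% is practically impossible. In any sparse cell the intervals can be misleading: at the planned rate, coverage is 55.8%, 81.9% and 85.3% with 5, 10 and 20 women per arm, limits can pass 100%, and an all-responder cell has zero width. How many displayed cells this affects cannot be determined from the documents. The zero width at 100% needs no assumption about the true rate; the coverage figures assume 83.6% or the stated range. The non-inferiority conclusion is unaffected.

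**What to change.** In SAP 7.1, state that 95% confidence intervals for a single proportion use the Wilson or the Clopper-Pearson method in place of Wald, and name that method in 7.8.1.1 (per arm), 7.8.1.2 and 7.8.1.4.

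Either choice is defensible. Wilson stays closer to 95% on average. Clopper-Pearson matches the phase 2 interval, so the two studies' rates could be set side by side, but it is conservative (about 96% to 99% in most cases run). Some intervals become wider: for 9/10, Clopper-Pearson runs from 55.5% to 99.7%, a width of 44.2 points against 37.2 for Wald. The choice should be fixed before unblinding.

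Leave unchanged the FM interval and test for the difference, and the hemoglobin difference intervals in 7.8.2.3. The cost is one sentence and a standard software option, with no effect on sample size, testing or data collection.
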